## **9 STUDY PROCEDURES**

This section provides a general description of the procedures and assessments associated with this study. The timing of the study procedures and the windows permitted for the assessments is presented in [Appendix 1](#).

During the COVID-19 pandemic, alternative methods for conducting study assessments should be considered when compliance, feasibility, and safety can be assured. These methods may include:

- Telemedicine visits, e.g., via telephone/video (using compliant video-conference tools as permitted by health authority regulations)
- Use of primary care centers and local laboratories for blood draws and imaging/radiographs

If alternative methods are used, local laboratory reference ranges will be documented and submitted to the sponsor. Local laboratory test results, laboratory accreditation (if possible), and reports of tumor assessments should be retrieved and documented in the participant's study records.

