## 9.8 Clinical Laboratory Tests

Blood and urine samples will be collected at the times specified in [Appendix 1](#). Hematology, chemistry, pregnancy, urinalysis, coagulation time, and endocrine evaluation tests (as applicable) will be performed locally. Test results for pregnancy, chemistry, and hematology must be reviewed prior to all infusions of MGC018. On the dosing days, clinical laboratory tests should be collected prior to administration of prophylactic pre-medications. Local laboratory tests to be performed are presented in [Appendix 2](#).

- A blood sample for local testing of the tumor marker PSA will be collected from participants with mCRPC. PSA measurements are performed at the times specified in [Appendix 1](#) and approximately every 12 weeks during the post-treatment follow-up period until disease progression, start of another cancer therapy, or the study cutoff date, whichever comes first.
- A blood sample for testosterone will be collected from participants with mCRPC in Cohort Expansion. Testosterone measurements are performed at the times specified in [Appendix 1](#) and approximately every 12 weeks during the post-treatment follow-up period until disease progression, start of another cancer therapy, or the study cutoff date, whichever comes first.

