## 11 ASSESSMENT OF EFFICACY

### 11.1 Efficacy Assessments

#### 11.1.1 Disease Response Assessments

Tumor assessments will be obtained using CT (or PET/CT) and/or MRI scans. For mCRPC participants a bone scan will be obtained in addition to CT and/or MRI scans at baseline and on study. Target and non-target lesions will be designated at screening and then evaluated at every 6 weeks (42 days) for the first four cycles, and every other cycle thereafter while the participant in Module A Dose Escalation and Module B is on study treatment; every 9 weeks (63 days) for Cohort Expansion Module A participants. For mCRPC a lymph node is to be  $\geq 20$  mm to be a target lesion. In situations where the bone scan findings are suggestive of a flare reaction or apparent new lesion(s) may represent trauma, additional imaging to confirm these results with other imaging modalities such as MRI or fine-cut CT should be obtained. At each tumor assessment time point, the overall response status will be determined based on assessment of target and non-target lesions as well as appearance of any new lesions. Radiographic disease progression in mCRPC is defined in [Section 14.6.4.1](#). Participants who discontinued from study treatment due to reasons other than documented, confirmed progressive disease, will be contacted every 3 months (90 days) during the Post-Treatment Follow-up period about the response status and survival of these participants, as applicable.

For RECIST v1.1 ([Appendix 5](#)), the overall responses will be categorized as Complete Response (CR), Partial Response (PR), Stable Disease (SD), Progressive Disease (PD), or Not Evaluable (NE). For participants who experience an objective response of CR or PR, responses will be considered unconfirmed until the response has been documented by a subsequent confirmatory scan obtained no less than 4 weeks after the initial scan demonstrating an objective response.

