### 14.1 Determination of Sample Size

The study plans to enroll approximately up to 182 participants (107 in Module A and 75 in Module B). This number of participants does not take into account participants who may be replaced for non-evaluable participants or the possibility of expanding the mCRPC cohort with an additional 24 participants at the discretion of the sponsor.

In Module A, 27 participants were enrolled, of which 26 participants were treated with MGC018 monotherapy in the Dose Escalation Phase. Up to 80 participants with mCRPC, NSCLC, TNBC, SCCHN, and melanoma (up to 16 in each) will be enrolled to the Cohort Expansion Phase of Module A. Up to an additional 4 participants may be added per cohort. In Module B, up to 27 participants will be enrolled in the Dose Escalation Phase based on a 3+3+3 design with planned 3 dose cohorts in MGC018 and MGA012 combination therapy. The Cohort Expansion Phase of Module B will enroll up to 16 participants into each of 3 tumor specific cohorts (SCCHN, mCRPC, and participants with a tumor type TBD at a later date) treated with MGC018 in combination with MGA012. The sample size for each tumor specific cohort is primarily based on providing preliminary estimation of responses. **Table 10** provides the 2-sided 95% confidence interval (CI) for a number of potential responses.

The sample size for the mCRPC cohort expansion is primarily based on providing preliminary estimation of a 6 month rPFS rate.

**Table 10** Response Rates and 95% Confidence Intervals

| Sample Size | Number of Responses | Response Rate (%) | 95% Confidence Interval (%) |
|-------------|---------------------|-------------------|-----------------------------|
| 16          | 1                   | 6.3               | 0.2, 30.2                   |
| 16          | 2                   | 12.5              | 1.6, 38.3                   |
| 16          | 3                   | 18.8              | 4.0, 45.6                   |
| 16          | 4                   | 25.0              | 7.3, 52.4                   |
| 16          | 5                   | 31.3              | 11.0, 58.7                  |
| 16          | 6                   | 37.5              | 15.2, 64.6                  |

During the Cohort Expansion Phase, participants who withdraw before completing the first tumor assessment for a reason other than clinical disease progression or death are considered unevaluable for response. In these cases, additional participants may be enrolled.

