| Serum Biomarkers (Cohort
Expansion only)                                                                                                                                                                                                                                                                                                                                            | See Appendix 3                  |               |       |                |                 |                 |                 |                               |                 |                                            |                     |                    |
| Anti-Drug Antibody (ADA)                                                                                                                                                                                                                                                                                                                                                               | See Appendix 3                  |               |       |                |                 |                 |                 |                               |                 |                                            |                     |                    |
| Tumor Assessment
(CT/PET/MRI (bone scan
for mCRPC))                                                                                                                                                                                                                                                                                                                              | X                                               | Every 9 weeks |       |                |                 |                 |                 |                               |                 | X                                          |                     |                    |

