| Urinalysis                                       | X                                                                                                                                                                                                                                                                                                                                                 | X       |              |                |        |                 |                                | X                                            |                 |                                 |                 | X                                           |                    |
|                                                         | To be collected pre-infusion and prior to prophylactic pre-medications on dosing days. Day 1 urine samples can be collected up to 1 day before infusion. See Appendix 2 for list of assessments. Collect as scheduled and as clinically indicated. Reflex test for microscopic evaluation if abnormal.                            |         |              |                |        |                 |                                |                                              |                 |                                 |                 |                                             |                    |
| PSA (mCRPC only)                                 | X                                                                                                                                                                                                                                                                                                                                                 |         |              |                |        |                 |                                | X                                            |                 |                                 |                 |                                             |                    |

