|                                                                                                                                                                                                                                                                                                                                                                                                                                                                                                   |                                              | Day 1   | Days 2 and 4 | Day 8
(±1d) | Day 15 | Day 22
(±1d) | Day 42 
(±3d) | Day 1
(±1d)                               | Day 22
(±1d) | Days 23, 25,
29, 36
(±1d) | Day 42
(±3d) |                                             |                    |
| Tumor Assessment
(CT/PET/MRI)                                                                                                                                                                                                                                                                                                                                                                                                                                                                  | X                                            |         |              |                |        |                 | X                              |                                              |                 |                                 | X               | X                                           |                    |
| Radiographic disease assessments will occur on Day 42 ± 3 days for the first four cycles, and every other cycle thereafter. Assessment will also be done at EOTV.                                                                                                                                                                                                                                                                                                                                 |                                              |         |              |                |        |                 |                                |                                              |                 |                                 |                 |                                             |                    |

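### The Module B visit schedule omits the mCRPC bone scan and serum testosterone that the protocol text requires, so bone progression may be missed or dated late and exclusion 28 has no scheduled test

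*Protocol*

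**What the plan says.** **Module B schedule (Appendix 1).** One table serves both dose escalation and expansion. Imaging is timed by the sentence "Radiographic disease assessments will occur on Day 42 ± 3 days for the first four cycles, and every other cycle thereafter", and the row label names CT, PET and MRI only. The one laboratory row specific to prostate cancer begins "PSA (mCRPC only". Neither a bone scan nor testosterone appears anywhere in the table.

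**Module A expansion schedule (Appendix 1).** The tumor-assessment label begins "CT/PET/MRI (bone scan" and goes on to name mCRPC. A serum testosterone row is marked from screening through follow-up.

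**Protocol text.** Section 11.1.1, like the synopsis, states: "For mCRPC participants a bone scan will be obtained in addition to CT and/or MRI scans at baseline and on study". Section 9.9 also calls for a bone scan in mCRPC, but for the Cohort Expansion Phase. Section 9.8 states: "A blood sample for testosterone will be collected from participants with mCRPC in Cohort Expansion", and refers to Appendix 1 for when. Appendix 2 lists testosterone by name for the Module B expansion. Exclusion 28 sets a testosterone limit for mCRPC in both expansion phases.

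**Role of Appendix 1.** Section 9 opens with: "The timing of the study procedures and the windows permitted for the assessments is presented in" Appendix 1.

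**Use of the data.** Section 14.6.4.1 of the protocol and Section 5.1.4 of the SAP count two or more new bone lesions as an rPFS event. Section 14.1 says: "The sample size for the mCRPC cohort expansion is primarily based on providing preliminary estimation of a 6 month rPFS rate". It does not limit this to one module. It also says: "The Cohort Expansion Phase of Module B will enroll up to 16 participants into each of 3 tumor specific cohorts", and mCRPC is one of the three.

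**The concern.** Sites usually plan visits from the schedule table. In Module B that table gives them no cue to order a bone scan or a testosterone test, although the text expects both.

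For rPFS the risk lies in the bone component. A lesion can be called new only against a comparable earlier image, and a baseline bone scan that was not done cannot be obtained later. If on-study bone scans are left out or done irregularly, progression that only a bone scan would show is missed or dated late. rPFS is a secondary objective in mCRPC with no module restriction. The Module B cohort may also enroll men without measurable disease (inclusion 6) and men who qualify on new bone lesions (inclusion 7), so bone matters in this population. The radiographic criterion in Section 5.4 draws on the same images.

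The testosterone gap is a separate matter. Section 5 allows no exceptions to eligibility, yet a site following the Module B table has no scheduled test with which to apply exclusion 28.

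**Working it through.** The plan gives no figure that depends on this point, so there is none to reproduce. The check is a comparison of passages, followed by an illustration of size.

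**Step 1. Side by side.**

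| Item for mCRPC | Module B table | Module A expansion table | Protocol text |
|---|---|---|---|
| Bone scan | Not named | Named: screening, every 9 weeks, end of treatment | Synopsis and 11.1.1: all mCRPC; 9.9: Cohort Expansion |
| Testosterone | No row | Row: screening, each dosing visit, end of treatment, follow-up | 9.8 (times left to Appendix 1), 9.17, Appendix 2, exclusion 28 |
| PSA | Row present | Row present | 9.8 |

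The Module B laboratory rows run directly from PSA to pharmacokinetics and the imaging label is complete, so this does not look like lost text.

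**Step 2. Does the text supply the timing?** For the bone scan, in part. Section 11.1.1 fixes a baseline scan. The sentence after it sets the lesion-assessment interval and names Module B, so the natural reading is that bone scans go with those visits. It is not stated. For testosterone, only the post-treatment interval is given (about every 12 weeks, 9.8 and 9.17). For screening and treatment, 9.8 sends the reader to Appendix 1, where the Module B table is silent.

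**Step 3. How many assessments are affected?** Six months is 6 × 365.25/12 = 182.6 days. Module B imaging falls on Days 42, 84, 126 and 168 (42 × cycle 1 to 4), so four assessments precede the 6-month mark, none with a listed bone scan. Module A expansion imaging falls on Days 63 and 126, each with a bone scan; the third, Day 189, is after 6 months.

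**Step 4. Size, as an illustration.** Let S be the true 6-month rPFS and b the share of the progression hazard that is visible only on bone scan. If hazards are constant and independent and none of that share is detected, the apparent rate is S^(1−b). The documents give neither S nor b, so both are assumed.

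- S = 0.50, b = 0.20: 0.50^0.80 = 0.574, a bias of 7.4 points.
- S = 0.50, b = 0.40: 0.50^0.60 = 0.660, a bias of 16.0 points.

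Over a wider range of assumptions:

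| True S | b = 0.10 | b = 0.25 | b = 0.50 |
|---|---|---|---|
| 20% | 23.5% | 29.9% | 44.7% |
| 40% | 43.8% | 50.3% | 63.2% |
| 50% | 53.6% | 59.5% | 70.7% |
| 60% | 63.1% | 68.2% | 77.5% |

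For any given S and b these are worst cases. They suppose that every site omits the scan and that CT, PET and MRI show none of these lesions.

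**The case against.** The best reply is that the protocol already requires both items. The synopsis, 9.9 and 11.1.1 call for the bone scan without excluding Module B; 9.8, 9.17 and Appendix 2 call for testosterone; and exclusion 28 cannot be applied without a value. Section 9 says where timing is shown. It does not say that a procedure required elsewhere lapses if the table omits it. All of this stands, and it makes the point a conflict between table and text rather than a missing requirement.

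A reader might infer that bone progression cannot be detected in Module B. The documents do not support that. The rPFS definition does not restrict new bone lesions to those found on bone scan. Section 9.9 has chest, abdomen and pelvis imaged by CT or PET/CT and/or MRI, and Appendix 5 (1.1.3) accepts PET and plain films to confirm that a bone lesion is present. What remains exposed is progression that only a bone scan would show, at sites that rely on the table alone.

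A reader might also tie the testosterone omission to rPFS. There is no such link.

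Finally, with at most 16 participants any estimate is imprecise: Table 10 gives 15.2% to 64.6% for 6 responses in 16. That limits what the cohort can show, but the interval does not account for a one-directional ascertainment error.

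**Conclusion.** The concern holds as an internal inconsistency. The Module B table omits two mCRPC assessments that the protocol text requires and that the Module A expansion table lists. The likely effect, where sites follow the table, is that some bone progression is missed or dated late. Module B mCRPC rPFS would then be too favorable and less comparable with Module A.

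The size cannot be derived from the documents. The figure of about 57–66% for a true 50% is an upper bound for an assumed bone-only share of 20–40%, not an expected bias. The upward direction rests mainly on missed on-study scans. If only the baseline scan were missed, the direction would depend on how the first on-study scan is read. Taken as the new reference, it hides earlier progression. Read under Appendix 5 (2.3.5), it could count lesions at sites not scanned at baseline as new.

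The testosterone omission is a distinct and narrower gap in eligibility screening and on-treatment timing.

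**What to change.** In the Module B table of Appendix 1:

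- Add a bone scan for mCRPC, labeled Cohort Expansion, to the tumor-assessment row at screening and at each scheduled assessment.
- Add a serum testosterone row for mCRPC, labeled Cohort Expansion, with visits matching the Module A expansion table.

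The expansion label is needed because this table also covers dose escalation, while 9.8 and 9.9 confine these items to expansion. Other rows in the table already carry such a label.

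Also reconcile 9.9 (expansion only) with 11.1.1 (all mCRPC participants), so that it is clear whether mCRPC participants in dose escalation need a bone scan.

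The cost is a correction to the schedule and one clarifying sentence. For the expansion cohort it adds no kind of test that the protocol does not already require. If any Module B mCRPC participants have already been imaged, record which of them lack a baseline or on-study bone scan before rPFS is analyzed.

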## Appendix 2 Clinical Laboratory Tests

|                                                                                                                                                                                                                                                                                                                                                                                                                                                                                                                                                                                                          |                                                                                                                                                                                                                                                                                                                                                                                                                                                                                                                                                                                                                                                                                                                                                          |
|----------------------------------------------------------------------------------------------------------------------------------------------------------------------------------------------------------------------------------------------------------------------------------------------------------------------------------------------------------------------------------------------------------------------------------------------------------------------------------------------------------------------------------------------------------------------------------------------------------|----------------------------------------------------------------------------------------------------------------------------------------------------------------------------------------------------------------------------------------------------------------------------------------------------------------------------------------------------------------------------------------------------------------------------------------------------------------------------------------------------------------------------------------------------------------------------------------------------------------------------------------------------------------------------------------------------------------------------------------------------------|
| 
Pregnancy test:
Blood or Urine Human chorionic gonadotropin (hCG)
 
Hematology (CBC with differential):
Hemoglobin
Hematocrit
Platelet count
White blood cell count
Absolute neutrophils, lymphocytes, and eosinophils
 
Serum chemistry:
Albumin
Alkaline phosphatase
Alanine aminotransferase
Aspartate aminotransferase
Bicarbonate
Bilirubin (Total and Direct)
Blood urea nitrogen
Calcium
Chloride
Creatinine
Glucose
Magnesium
Phosphate
Potassium
Sodium
Uric acid
 | 
Coagulation:
Prothrombin time (PT) – preferred, or INR is acceptable
International normalised ratio (INR)
Partial thromboplastin time (PTT)
 
Endocrine tests:
Free thyroxine (Module A Dose Escalation and Module B Dose Escalation and Module B Cohort Expansion)
Thyroid-stimulating hormone (Module A Dose Escalation and Module B Dose Escalation and Module B Cohort Expansion)
Serum testosterone (mCRPC Module A Cohort Expansion and Module B Cohort Expansion)
 
Urinalysis:
Protein
Occult blood
If abnormal protein or occult blood, perform reflex test for microscopic evaluation
 
Tumor marker:
Prostate specific antigen (PSA) for mCRPC only
 |
|----------------------------------------------------------------------------------------------------------------------------------------------------------------------------------------------------------------------------------------------------------------------------------------------------------------------------------------------------------------------------------------------------------------------------------------------------------------------------------------------------------------------------------------------------------------------------------------------------------|----------------------------------------------------------------------------------------------------------------------------------------------------------------------------------------------------------------------------------------------------------------------------------------------------------------------------------------------------------------------------------------------------------------------------------------------------------------------------------------------------------------------------------------------------------------------------------------------------------------------------------------------------------------------------------------------------------------------------------------------------------|

